If the patient is interested in participating in the study, but unable to complete the study after the clinic visit (e.g., time constraints, first contact with patient navigator is over the telephone, RA is not on site), the patient can provide the healthcare professional (physician or patient navigator) with permission to be contacted by the study research team. The healthcare provider (e.g., patient navigator or physician) will then give the research staff the patient's preferred contact information. The research staff members will then contact the patient to arrange for a convenient time to meet to complete the consent and intervention.

b) Inclusion and Exclusion Criteria

Eligibility criteria include: 1) self-identify as Black/African American; 2) received a referral for a screening colonoscopy; and 3) English speaking

Healthcare providers (e.g., primary care physicians and gastroenterologists) will determine whether the patient is medically eligible for a screening colonoscopy (e.g., age eligible for a screening colonoscopy based on published guidelines).

Exclusion include: 1) hearing or vision impaired; 2) Phase I participant

c) Number of Subjects

200 participants (100 per condition)

d) Study Timelines

The total study duration is 5 years (September 2015-October 2020).

Years 1-2: Create and field test e-Motivate

Years 3-4: Enroll participants in RCT (Phase II)

 Mount Sinai	Protocol Name:	Internet-based Motivational Interviewing for Colonoscopy in African Americans
	Principal Investigator:	[name]
	Primary Contact Name/Contact Info:	[name], [contact] ,
	Date Revised:	8/16/19
	Study Number:	GCO# 14-0275 IF# HS#

Years 4-5: Conduct follow up medical chart reviews. Conduct qualitative follow up interviews. Conduct all data analyses.

e) Endpoints

Participants in the RCT will have their medical charts reviewed, six months following the initial referral, to determine if the colonoscopy has been completed. Secondary outcomes (e.g., bowel prep quality, number of cancellations) will also be recorded. Participants will also complete a demographics assessment and a questionnaire that assesses mediators (autonomy, competence, relatedness).

There are no events/results that would cause a study subject's participation to end due to safety.

f) Procedures Involved in the Human Research

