each recruitment day, the RAs will use the CERNER list and EMR to review patients' race, age, and previous colonoscopy history. RAs will alert healthcare providers (e.g., physicians and patient navigators) daily of patients who may be eligible for a screening colonoscopy referral. If a patient is eligible for the study (e.g., self-identifies as black/African American, age-eligible for CRC screening, and received a referral for a screening colonoscopy), the physician or patient navigator will briefly introduce the study to the patients at the end of the primary care or GI appointment. Patients who are interested in participating in the study will meet with an RA in a private exam room immediately following their appointment to review and complete the consent form.

If the patient is interested in participating in the study, but unable to complete the study after the clinic visit (e.g., time constraints, first contact with patient navigator is over the telephone, RA is not on site), the patient can provide the healthcare professional (physician or patient navigator) with permission to be contacted by the study research team. The healthcare provider (patient navigator or physician) will then give the research staff the patient's preferred contact information. The research coordinator will then contact the potential participant and schedule a date/time to complete the consent form.

Consented participants will complete a verbally administered baseline questionnaire. Participants will then be assigned to one of two groups: e-Motivate (N=100) or control group (N=100). Participants assigned to e-Motivate condition will receive usual care and will also complete the 20 minute e-Motivate app. Immediately after completing the e-Motivate app, the RA will verbally administer a post-intervention questionnaire that assesses the hypothesized mediators. Participants in the control group will receive usual care (e.g., patient navigation, print materials). Participants will receive \$20 gift card to Target as compensation. Six months following the initial referral, medical charts will be reviewed to determine whether the colonoscopy was completed, the quality of the bowel prep, and process variables (e.g., number of cancellations/rescheduled appointments/no-shows)

g) Specimen Banking

N/A

h) Data Management and Confidentiality

Survey Data:

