Throughout the study, quantitative survey data will be collected. The survey data will be scanned and uploaded on our Department's secure internet server (J drive). The hard copies of the surveys will be stored in a locked filing cabinet in the CAM building. Each participant's data will be de-identified and assigned an anonymous ID number. A "cross-over" file matching ID number with participant identifying information (name, address and phone number) will be maintained and stored separately on our department's secured and encrypted intranet server. Only study personnel will have access to the crossover file.

 Mount Sinai	Protocol Name:	Internet-based Motivational Interviewing for Colonoscopy in African Americans
	Principal Investigator:	[name]
	Primary Contact Name/Contact Info:	[name], [contact] ,
	Date Revised:	8/16/19
	Study Number:	GCO# 14-0275 IF# HS#

CERNER Data:

In addition, as part of the RCT, we will first obtain the CERNER list to identify the Black/African American patients who are age eligible or CRC screening and are scheduled for a primary care or GI appointment that day. We will then access EMR to identify whether the patient may be eligible for a screening colonoscopy (has not had a recent screening colonoscopy procedure in the EMR). We have requested a HIPAA waiver. We will then alert the physicians and patient navigators of the patients who may be eligible or our study. The CERNER list will be destroyed at the end of each recruitment shift.

App Engagement Data:

We will record participants' engagement with e-Motivate. The e-Motivate will be linked to an electronic database that will be entirely anonymous and will only record the participants' overall engagement (e.g. responses to the exercises, amount of time spent on each exercise, etc.). The database will initially be stored on the AppLab's encrypted server. The anonymous dataset will then be sent to the Mount Sinai investigative team.

Outcome Data:

Six months following the initial visit, we will check the medical records of all consented participants in Phase II to obtain outcome data (e.g., colonoscopy completion status, prep quality, # of cancellations/rescheduled appointments/no-shows, receipt of PN/care coordination). The medical information will be de-identified and stored on a password protected file on Mount Sinai's intranet server.

DATA ANALYSES

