Missing data: The e-Motivate is a one-time intervention and thus we anticipate minimal missing data. *Analyses of covariates:* Participants will be randomly assigned to treatment condition and therefore significant baseline differences are not expected. However, contingency tables and t-tests will be performed to determine any differences between the two groups. Using a p value of ≤ 0.15 , any consistent pattern of correlation for any of the covariates would suggest their inclusion in the primary data analysis model.

Analysis of Primary Outcome: The primary outcome (screening uptake) will be assessed with a logistic regression model. The hypothesized moderators will be evaluated individually. The final logistic model will contain the main effect for the treatment group, any identified covariates, and any significant moderators.

Analysis of Secondary Outcome: If bowel prep quality is normally distributed, a t-test will be used to compare the two treatment groups.

Exploration of Mediation: In the mediation analyses, we will first show that treatment predicts the primary outcome. We will next evaluate the extent to which the treatment affects the mediators using a linear mixed model with repeated measures. Time will be entered into the model first followed by any covariates. Next, the binary treatment vector will be introduced as a main effect followed by interaction with time. Since there are three

 Mount Sinai	Protocol Name:	Internet-based Motivational Interviewing for Colonoscopy in African Americans
	Principal Investigator:	[name]
	Primary Contact Name/Contact Info:	[name], [contact] ,
	Date Revised:	8/16/19
	Study Number:	GCO# 14-0275 IF# HS#

correlated mediators, the p-values will be adjusted using the Sidak correction for multiple comparisons. Only the mediators that are predicted by the treatment main effect or the time by treatment interaction will be retained. Each mediator will then be introduced into the logistic model predicting the primary outcome. To establish mediation, the indirect paths from treatment to mediators and from mediators to outcomes will be assessed using 1000 bootstrap samples following the procedures.

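### Only the e-Motivate arm has a scheduled post-assignment mediator questionnaire, but the exploratory mediation analysis needs one in both arms

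*Combined protocol and SAP*

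**What the plan says.** **Assessment schedule (section 5f, RCT Procedures).** Before assignment: "Consented participants will complete a verbally administered baseline questionnaire". After assignment, in the e-Motivate arm: "Immediately after completing the e-Motivate app, the RA will verbally administer a post-intervention questionnaire that assesses the hypothesized mediators". The next sentence covers the other arm: "Participants in the control group will receive usual care (e.g., patient navigation, print materials"). No further questionnaire is listed for controls. The six-month follow-up is chart review only.

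**Other statements about questionnaires.** Section 5e says of RCT participants in general: "Participants will also complete a demographics assessment and a questionnaire that assesses mediators (autonomy, competence, relatedness"). It gives no time point and no repeat. Section 5h, Survey Data, says: "Throughout the study, quantitative survey data will be collected". It names neither an arm nor a time point.

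**Analysis (section 5h, Exploration of Mediation).** "We will next evaluate the extent to which the treatment affects the mediators using a linear mixed model with repeated measures". The order of entry is time, covariates, treatment, and last the interaction of treatment with time. P-values are Sidak-adjusted because there are three correlated mediators. A mediator is retained if either the treatment term or the interaction predicts it. Retained mediators enter the logistic model for uptake, and the indirect path is bootstrapped with 1000 samples. The plan does not say which mediator score (baseline, post or change) enters the logistic model.

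**Status.** Mediation belongs to Exploratory Aim 2b (section 1).

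**The concern.** A mediation analysis asks whether the app moved autonomy, competence or relatedness more than usual care did, and whether that movement carries through to colonoscopy uptake. The first question needs a mediator score after assignment in the control arm, and 5f does not schedule one. Charts reviewed at six months cannot supply it later.

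If staff follow 5f, the interaction that section 5h relies on has no data behind it. A mediator could then be retained only through a chance baseline difference between arms, whatever the app does. At stake is the mediation half of Aim 2b.

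**Working it through.** **1. The plan's own figure.** No power or sample size is given for mediation. The only stated power, 0.83, is for uptake (71.4% against 52%, 100 per arm, alpha 0.05, two-sided assumed). With unpooled variance: SE = sqrt(0.714×0.286/100 + 0.52×0.48/100) = 0.0674; 0.194/0.0674 − 1.96 = 0.92; power 0.82. With pooled variance it is 0.81. The stated figure reproduces within two points, and nothing below depends on it.

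**2. Which cells are observed.** Inputs are 100 per arm (section 5c) and the schedule in 5f. Assumption: the baseline questionnaire includes the mediator scales in both arms, which 5f does not state. Code control/e-Motivate as 0/1 and baseline/post as 0/1. The model mean is b0 + b1·time + b2·treatment + b3·time×treatment.

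| Cell | Scheduled | Mean |
|---|---|---|
| Control, baseline | yes | b0 |
| e-Motivate, baseline | yes | b0 + b2 |
| e-Motivate, post | yes | b0 + b1 + b2 + b3 |
| Control, post | no | b0 + b1 |

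Scores per mediator: 3×100 = 300 of 4×100 = 400.

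**3. What can be estimated.** Three cell means cannot identify four coefficients. The design matrix has rank 3 of 4 (5 of 6 with two covariates), which leaves 0 degrees of freedom for the interaction. Only the sum b1 + b3, the mean change in the e-Motivate arm, is identified. Forcing a common baseline mean (b2 = 0) does not help, because time and time×treatment are still the same column. With the fourth cell the rank is 4 of 4.

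**4. What the treatment term measures.** With three cells, b2 is the baseline difference between arms. In 200 simulated datasets (100 per arm, within-person correlation 0.6, two covariates), app effects of 0, 0.3, 0.5 and 0.8 SD were added to the e-Motivate post scores. The time coefficient rose by exactly that amount. The treatment coefficient did not change, and stayed within 0.016 SD of the covariate-adjusted baseline difference.

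**5. The indirect path.** Complete cases on the post score are all e-Motivate, so treatment is constant and has no coefficient. The baseline score precedes assignment and cannot carry a treatment effect. Bootstrapping does not create the missing contrast.

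**6. Secondary check: the retention rule if all four cells exist.** The number of p-values in the Sidak adjustment is not stated, so both readings are shown.
- Over three: level 1 − 0.95^(1/3) = 0.01695. If the treatment term is tested before the interaction enters, the two tests are uncorrelated under the null, and false retention per mediator is 1 − (1 − 0.01695)² = 0.0336. If it is read from the interaction model, false retention is 0.0318 to 0.0326 for assumed pre-post correlations of 0.5 to 0.7. That is 3.2% to 3.4% against 1.7%.
- Over six: level 1 − 0.95^(1/6) = 0.0085, and 1 − (1 − 0.0085)² = 0.0169. The excess disappears.

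**7. Power of one baseline-adjusted test (Sidak over three) against the two routes**, with both arms measured and an assumed 0.3 SD effect:

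| Assumed pre-post correlation | Two routes | Adjusted test |
|---|---|---|
| 0.6 | 50% to 55% | 60% |
| 0.8 | 84% to 85% | 87% |
| 0.9 | 99% | 99% |

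**The case against.** The strongest reply is that this is a drafting omission. Section 5f never says that controls are not reassessed, 5e attaches the mediator questionnaire to RCT participants rather than to one arm, and a time-by-treatment model makes sense only if both arms are measured twice. That is plausible, and it means the documents do not support the inference that the trial chose to leave controls unassessed, or that controls were in fact not assessed. The gap still stands. The baseline questionnaire alone would satisfy 5e, and an assessment that staff must infer from the analysis section is not in the procedures they follow.

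A reader might also infer that the retention rule doubles the error rate even with controls reassessed. The documents do not support that as a general statement. It holds only if Sidak is taken over three tests, which is the natural reading but is not stated. Nor is it an error rate for mediation claims: retention is a gate, preceded by a required treatment effect on uptake and followed by the bootstrapped indirect path.

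It is also fair to say that, with both arms measured, the planned interaction test is valid. The power advantage of the baseline-adjusted test is modest and vanishes at high pre-post correlation, which is plausible for a retest in the same session.

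**Conclusion.** Sections 5f and 5h are inconsistent and should be reconciled. If 5f is followed, with the scales at baseline in both arms, the mediation analysis cannot be estimated: one arm-by-time cell is empty, the interaction is aliased with time, the treatment term reflects only the pre-assignment difference, and post scores exist in one arm. If the baseline questionnaire omits the scales, the position is worse, because 5f then schedules no mediator score for controls at all.

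The consequence depends on what is actually done with controls, which the documents do not say. It is confined to the mediation part of an exploratory aim. It would be wrong to infer any harm to the trial's main result: uptake and bowel-prep quality come from charts in both arms, and the moderator analyses do not use a post-assignment questionnaire.

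The retention-rule figures are a secondary note that rests on an assumed number of adjusted tests and assumed correlations.

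**What to change.** 1. **Confirm, then state.** Establish whether controls complete the mediator scales after assignment. If they do, say so in 5f and state that the scales are also in the baseline questionnaire. If they do not, have controls still to be enrolled complete them again in the same session, at an interval matched to the app (up to 20 minutes). Section 9 already places consented participants in a private room with the RA.
2. **Amend section 5h.** Test the treatment-to-mediator path by regressing the post score on treatment, adjusted for the baseline score: one test per mediator, with Sidak over three. Remove retention on the treatment term, because it can reflect baseline imbalance. Name the post score as the value entered in the logistic model.
3. **Fallback.** If controls were not reassessed and too few remain to enrol, drop the mediation claim and report mediator change descriptively within the e-Motivate arm.

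**Cost.** Confirmation and items 2 and 3 are wording only. Reassessing controls needs an amendment and a few minutes of RA time for each control. Repeated questions may prompt controls, and late controls would be handled differently from earlier ones; the report should say so. It may also reach few people. The timeline reads "Years 3-4: Enroll participants in RCT (Phase II"), and four years from September 2015 end at about the document date of 8/16/2019. Actual accrual is not stated, so the fallback may be the realistic course.

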Primary objective: To conduct an RCT that examines the efficacy of e-Motivate versus a control condition for increasing screening colonoscopy uptake in Black/African Americans. Black/African American patients referred for a screening colonoscopy will be recruited to the RCT. Participants (N=200) will be randomly assigned to an e-Motivate group (N=100) or a control group (N=100). Participants in e-Motivate group will receive usual care and will also complete a one-time, 20-minute e-Motivate app on a tablet immediately following the primary care appointment in which they received a referral for a screening colonoscopy. Participants in the control group will receive usual care (e.g., print handout, patient navigation). It is hypothesized that participants in e-Motivate condition will be more likely to complete the recommended screening colonoscopy.

 Mount Sinai	Protocol Name:	Internet-based Motivational Interviewing for Colonoscopy in African Americans
	Principal Investigator:	[name]
	Primary Contact Name/Contact Info:	[name], [contact] ,
	Date Revised:	8/16/19
	Study Number:	GCO# 14-0275 IF# HS#

Exploratory Aim 2a. To explore the efficacy of e-Motivate for improving a secondary adherence outcome (e.g., bowel prep quality).

Exploratory Aim 2b. To explore mediators and moderators of e-Motivate. As a part of the RCT, potential mediators (i.e., competence, autonomy, relatedness) and moderators (i.e., demographics, Internet fluency/use) will be explored.

2) Background

Colorectal cancer (CRC), a largely preventable disease, remains the second cause of cancer death in the United States in men and women combined. Compared to other racial groups, Black/African Americans have the highest CRC morbidity and mortality rates. Given these disparities, it is critical to increase Black/African Americans' participation in CRC prevention efforts.

A motivational interviewing (MI) intervention can help improve Black/African Americans' screening colonoscopy uptake. MI is a brief patient-centered intervention that increases perceived competence, autonomy, and relatedness in order to promote behavioral change. Extensive research supports the efficacy of MI to promote preventive health screening uptake (e.g., increase HIV testing) and MI has proven efficacious with Black/African Americans across a wide range of diseases. There is strong support for the use of MI to improve Black/African Americans' screening colonoscopy uptake.

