Analysis of Power: We are proposing a sample of 200 participants (100 in each treatment arm) and setting alpha equal to 0.05. In our pilot study, the MI condition was associated with 71.4% (20/28) screening uptake compared to 52.0% (13/25) for the control condition. Based on these results, we are hypothesizing that approximately 71.4% of participants in e-Motivate condition will complete the colonoscopy, compared to approximately 52% of the participants in the control condition. Based on these projections, power is equal to 0.83. Of note, for the proposed study, the control condition will be a print brochure. Previous research suggests that a print brochure produces comparable CRC screening rates (52.0%-53.5%) to our pilot study's attention control condition (52.0%).

i) Provisions to Monitor the Data to Ensure the Safety of Subjects

Part I: Elements of a Data and Safety Monitoring Plan

1. List the name(s) of the individual(s) at the Mount Sinai School of Medicine (MSSM) who will be responsible for data and safety monitoring of this study. For each individual, indicate their role, name, title, and department information.

MSSM Principal Monitor:

Check One: PI: Team Member: Independent:

Last Name: [name]

First Name: [name]

Academic Title: Instructor

Department: Oncological Sciences

Mailing Address: [name]

[contact]

[contact]

E-mail: [contact]

MSSM Additional Monitor:

Check One: PI: Team Member: Independent:

Last Name: [name]

First Name: [name]

Academic Title: Professor

Department: Oncological Sciences

Mailing Address: [name]

[contact]

 Mount Sinai	Protocol Name:	Internet-based Motivational Interviewing for Colonoscopy in African Americans
	Principal Investigator:	[name]
	Primary Contact Name/Contact Info:	[name], [contact] ,
	Date Revised:	8/16/19
	Study Number:	GCO# 14-0275 IF# HS#

[contact]
E-mail: [contact]

2. Justify your choice of principal monitor in terms of the assessed risk to the research subject's health and wellbeing. In high risk studies when the principal monitor is independent of the study staff, indicate the individual's credentials, relationship to the PI, and the rationale for selection.

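### Exploratory moderators selected on the trial data enter the final primary model, which can change the treatment effect being tested and push its type I error above 5%

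*Combined protocol and SAP*

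**What the plan says.** Section 1 (Objectives) states one primary hypothesis, about uptake in the whole randomised comparison: "It is hypothesized that participants in e-Motivate condition will be more likely to complete the recommended screening colonoscopy". Moderators appear only under Exploratory Aim 2b: "moderators (i.e., demographics, Internet fluency/use) will be explored".

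The power paragraph in section 5h follows the same overall contrast. It projects "approximately 71.4% of participants in e-Motivate condition will complete the colonoscopy, compared to approximately 52% of the participants in the control condition" and adds: "We are proposing a sample of 200 participants (100 in each treatment arm) and setting alpha equal to 0.05". It does not mention moderators.

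The Analysis of Primary Outcome paragraph names logistic regression and continues: "The hypothesized moderators will be evaluated individually". It then ends: "The final logistic model will contain the main effect for the treatment group, any identified covariates, and any significant moderators".

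The plan gives no list of moderators beyond the two domains in Aim 2b. It gives no significance threshold or multiplicity adjustment for them, no coding, and no statement of whether they enter as interactions or main effects. The Sidak correction covers only the three mediators, and the 0.15 threshold covers only covariates. No model is named as the source of the primary p-value.

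**The concern.** A selection step that belongs to an exploratory aim sits inside the only confirmatory analysis. A moderator, in the ordinary sense, is a variable that interacts with treatment. Once a treatment-by-moderator term is in a logistic model, the treatment coefficient is the effect among patients whose moderator equals zero. For a 0/1 variable that is the reference category. For age in years it is a point where nobody is enrolled. Neither is the overall effect in the hypothesis and the power statement.

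Whether the tested effect changes in this way depends on which interactions reach significance, often by chance. Two analysts who follow the paragraph on the same data can then test different effects simply because they chose different reference levels. The stated alpha need not hold, and power can move in either direction. The mediation analysis inherits the ambiguity, since it starts from this step: "In the mediation analyses, we will first show that treatment predicts the primary outcome". It does not say from which model.

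**Working it through.** **Inputs from the document.** 100 per arm; alpha 0.05 (sidedness not stated, taken as two-sided); uptake 71.4% vs 52%; stated power 0.83; no allowance for missing outcomes.

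**Assumptions not in the document.** K independent 0/1 moderators at 50% prevalence with no true effect; an interaction is kept if its Wald p<0.05. Other settings follow below.

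**1. The plan's own figure.** Two-sided normal approximation with pooled null variance:
- mean rate = (0.714 + 0.52)/2 = 0.617
- null SE = √(2 × 0.617 × 0.383/100) = 0.0687
- alternative SE = √[(0.714 × 0.286 + 0.52 × 0.48)/100] = 0.0674
- z = (0.194 − 1.96 × 0.0687)/0.0674 = 0.880, so power = 0.810

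This is within 2 points of 0.83. It is the power of the overall contrast with no moderator in the model.

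**2. Mechanism, one candidate, no true effects.** With a balanced 0/1 moderator, the treatment estimate at m = 0 uses half the patients. Its correlation with the interaction estimate is −1/√2 = −0.71. A chance interaction therefore brings an extreme treatment estimate with it. From the bivariate normal, P(|z at m=0| > 1.96 given |z interaction| > 1.96) = 0.34. The exact type I error of the unadjusted Wald test at 52% in both arms is 5.58%. Hence:

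type I error ≈ 0.95 × 0.0558 + 0.05 × 0.34 = 0.070

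**3. Simulation of the procedure.** Each run fits logit(y) on treatment, m and treatment × m for each candidate. It keeps interactions with p<0.05, refits with all kept m and treatment × m terms, and tests the treatment coefficient at m = 0. There were 20,000 runs per scenario (Monte Carlo SE about 0.2 points for type I error, 0.3 for power). False benefit is the part of the type I error that favours e-Motivate.

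| K | Chance of keeping at least one null moderator, 1 − 0.95^K | Type I error | False benefit | Power |
|---|---|---|---|---|
| 1 | 5.0% | 6.8% | 3.5% | 79.7% |
| 2 | 9.8% | 8.3% | 4.0% | 78.2% |
| 3 | 14.3% | 9.9% | 5.1% | 76.9% |
| 4 | 18.5% | 10.8% | 5.6% | 75.4% |
| 6 | 26.5% | 13.2% | 6.8% | 72.6% |
| Treatment only | – | 5.2-5.7% | 2.6-3.0% | about 81% |

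A separate simulation (10,000 null trials per setting) gives type I error of 7.0%, 9.7% and 13.6% for K = 1, 3 and 6.

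**4. Entry and coding.** Under the null:
- mean-centred interactions: 5.2-5.7%
- main effects only: 5.1-5.7%
- ±0.5 coding: 5.2-5.7% at 50% prevalence, but up to 8.4% with six candidates at 30/70 prevalence

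**5. Sensitivity.**
- Threshold 0.01, 0.10 or 0.15 with K = 3: 7.2%, 11.5%, 12.2%.
- Six candidates: 10.1% if the reference level holds 70% of patients, 16.8% if it holds 30%.
- Raw scales: age alone (assumed mean 58, SD 6) 10.0%; a 1-5 Internet item alone 8.3%; both plus four binary moderators 17.4%.

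**6. One real moderator.** Control uptake is 52% in both of two equal-sized levels. Treated uptake is 61.5% and 81.3%, mean (61.5 + 81.3)/2 = 71.4%. The interaction log odds ratio is ln(0.813/0.187) − ln(0.615/0.385) = 1.47 − 0.47 = 1.0, and it is retained in about 37% of trials. Power is 51.9% if the weaker-effect level is the reference and 88.0% if the stronger-effect level is, against 81.0% for treatment only. At log odds ratio 0.5 it is 70.4% or 83.5%, against about 81%.

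**The case against.** The inflation needs three things the plan does not state: interaction terms, uncentred coding, and the coefficient at zero taken as the primary test. Where this plan wants an interaction it says so, as with treatment by time in the mediation paragraph. The primary paragraph opens with a plain logistic regression, so the final model could be a later model-building step after the treatment test. With one or two binary candidates the effect is modest: false benefit of 3.5-4.0% against 2.6-3.0%, and a power loss of about one to three points. The largest figures need six candidates, raw scales or an assumed strong interaction. Most null trials retain no moderator.

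Much of this stands as a limit on size. The figures are illustrative, and main-effects-only or mean-centred entry would leave the test sound. It does not settle the text. The plan lists moderators separately from covariates, calls the treatment term a main effect, and places the moderator-containing model under the primary outcome as the final one. Nowhere does it name another model as the primary test. The error rates above already average over the trials that retain nothing.

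**Conclusion.** The concern holds, in conditional form. The plan lets exploratory, data-selected moderators into the final primary model without fixing the effect to be tested. On the ordinary reading (interactions) with uncentred 0/1 coding, two-sided type I error is about 7% with one candidate, 10% with three and 13% with six. Power falls by about one to eight points when no moderator is real. If one is real, power can fall or rise with the reference level. These sizes rest on the assumed number, independence, prevalence and threshold of the moderators. That the plan leaves the primary model and contrast open does not depend on those assumptions. This should be fixed before the outcome data are analysed.

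**What to change.** State that the primary efficacy test is the treatment coefficient in one prespecified logistic model of six-month colonoscopy completion, containing treatment and any baseline covariates named in advance, with no treatment-by-moderator terms. Fit each moderator in its own exploratory Aim 2b model (treatment, moderator, interaction), and do not carry selected interactions back into the primary model. Naming covariates in advance would replace the plan's 0.15 selection rule, whose effect was not evaluated here.

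If the sponsor prefers to keep interactions in the final model, prespecifying mean-centred coding or a marginal treatment effect would also protect the test. The separate models are simpler and match the stated aims.

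The cost is SAP wording only. No patients or data are added, and every moderator result is still reported under Aim 2b.
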